## **8.2. Handling of Dropouts/Missing data**

For the primary efficacy outcome measure of overall response, patients with missing data or who are lost to follow-up will be considered as an indeterminate response and are included in the denominator for the calculation of overall success rate. Thus, patients with an indeterminate outcome are considered as failures for the primary analysis. A clinical failure occurring at an earlier time point will be carried forward to the subsequent visits.

In cases of missing or incomplete dates (e.g. AE and concomitant medications), the missing component(s) will be assumed as the most conservative value possible. For example, AEs with missing start dates, but with stop dates either overlapping into the treatment period or missing, will be counted as treatment-emergent, taking the worst-case approach. When partial dates are present in the data, both a partial start date and/or a partial stop date will be evaluated to determine whether it can be conclusively established that the AE started prior to the start of study drug or ended prior to the start of study drug. If the above cannot be conclusively established based on the partial and/or present dates, then the AE will be considered as treatment-emergent. Actual data values as they appear in the original eCRF will be presented in the data listings.

Missing values for other variables will not be imputed and only observed values will be used in data analyses and summaries.

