6.3.7 Day 7 to Day 14/End of Treatment Visit

Patients will be treated for 7 days (28 doses), with a prolongation of therapy up to 14 days if clinically indicated in patients with concurrent bacteremia. If EOT occurs on Day 7, Day 7 study procedures may be considered the EOT Visit study procedures. Day 7 to Day 14 study procedures are only required if the patient receives IV study treatment on Day 7 to Day 14. If EOT has already occurred, study procedures are not required to be performed. The EOT Visit will be completed on the final dosing day or the following day (allowing for a 1-day window to complete EOT procedures).

The following procedures will be performed at Day 7 to Day 14 and at the EOT Visit:

- Record concomitant medications;
- Perform a complete physical examination, including weight (Day 7 and EOT Visit only);
- Perform a limited physical examination (Day 8 to Day 14 only);
- Obtain vital signs, including blood pressure, heart rate, and respiratory rate;
- Assess clinical signs and symptoms;
- Assess clinical outcome (Day 7 and EOT Visit only);
- Perform pregnancy test for women of childbearing potential only (EOT Visit only);
- Collect blood sample for:
 - Serum chemistry (Day 7 and EOT Visit only);
 - Hematology (Day 7 and EOT Visit only); and
 - Blood cultures, if applicable;
- Collect urine sample by clean-catch midstream or other appropriate method that minimizes risk of bacterial contamination for:
 - Urinalysis (Day 7 and EOT Visit only); and
 - Urine cultures;

- Administer imipenem/cilastatin;
- Administer study drug; and
- Assess adverse events.

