6.5 Late Follow-up Visit

The LFU Visit will occur 7 days (± 2 days) following the TOC Visit. The LFU Visit should be performed as an in-office visit; however, if the patient is unable to attend the LFU Visit at the site, the patient may be contacted by telephone call for follow-up assessment of concomitant medications, clinical signs and symptoms, and adverse events.

The following procedures will be performed at the LFU Visit:

- Record concomitant medications;
- Perform a limited physical examination;
- Obtain vital signs, including blood pressure, heart rate, and respiratory rate;
- Assess clinical signs and symptoms;

- Assess clinical outcome;
 - Note: if a patient is a clinical failure at EOT, the patient is automatically considered a failure at the TOC Visit and LFU Visit, and the assessment of clinical response by the Investigator should be listed as “failure at EOT or TOC.”
- Collect blood samples for:
 - Serum chemistry;
 - Hematology; and
 - Blood cultures, if applicable;
- Collect urine sample by clean-catch midstream or other appropriate method that minimizes risk of bacterial contamination for:
 - Urinalysis; and
 - Urine cultures; and
- Assess adverse events.

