Day 1 is defined as the first day of study drug administration. The subsequent study days are defined by the number of calendar days thereafter. The duration of antibiotic treatment with study drug therapy will be 7 days (28 doses), with a prolongation of therapy up to 14 days if clinically indicated in patients with concurrent bacteremia.

All patients should receive at least 8 doses of IV study drug before the Investigator considers the patient to be a clinical failure and discontinues the patient from study drug therapy. No oral switch option is allowed. Patients who withdraw from study drug dosing should perform all End of Treatment (EOT) Visit procedures and should be followed through the Late Follow-up (LFU) Visit for safety assessments, even if they withdraw from dosing due to clinical failure.

Throughout the study, all patients will be monitored for signs and symptoms of cUTI or AP and the occurrence of adverse events. Laboratory data, including chemistry panels, complete blood counts, and samples for urine and blood cultures, as well as electrocardiograms (ECGs), will be collected from all patients at specified times throughout the study.

Sparse pharmacokinetic (PK) sampling (ie, a total of 5 samples per patient) will be performed to refine the population PK model. To maintain the blind, PK samples will be collected from both treatment groups. Samples obtained from the ETX2514SUL group will be analyzed using a validated assay by a central bioanalytical laboratory.

Patients will be enrolled in the study for approximately 21 days, with a maximum duration of study participation of 30 days. Screening procedures can be performed as standard of care within 48 hours prior to randomization on Day 1, with the exception of local laboratory serum creatinine determination, which must be obtained at the local laboratory within 24 hours of the first dose of study drug. The Treatment Period begins on Day 1, and study drug will be administered for 7 calendar days (or up to 14 days in patients with concurrent bacteremia). The EOT Visit will be completed on the final dosing day or the following day (allowing for a 1-day window to complete EOT procedures). The TOC Visit will be completed 7 days ( $\pm 1$  day) after the EOT for all patients. The LFU Visit will be completed 7 days ( $\pm 2$  days) after the TOC Visit for all patients.

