- Obtain medical/surgical history, including urological history; record inactive conditions diagnosed within the previous 5 years, complete urological/renal history, and all active conditions.
- Reasonable effort will be made to determine all relevant treatments (including all antibiotics, prescription and non-prescription medications, herbal medications, and vitamin supplements, supportive therapies, and non-pharmacologic treatments) received within 14 days before the first dose of study drug and during the study.
- Demographic data will be collected, including sex, age, race, and ethnicity.
- Complete physical examination includes weight (and height at Screening only). Limited physical examination does not include weight.

8. A complete physical examination is required on Day 7 and at the EOT Visit only. A limited physical examination should be performed on Day 8 to Day 14 if the patient has received blinded study drug.
9. Vital signs include blood pressure, heart rate, and respiratory rate.
10. If a patient is a clinical failure at EOT, the patient is automatically considered a failure at the TOC and LFU Visits, and the assessment of clinical response by the Investigator should be listed as "failure at EOT."
11. Day 7 and EOT Visit only.
12. A highly sensitive urine or serum pregnancy test will be performed at Screening, before the first dose of study drug, and at EOT for women of childbearing potential. If Screening occurs within 48 hours of randomization, study procedures performed at Screening do not need to be repeated.
13. EOT Visit only.
14. See Protocol Appendix B for a full list of clinical laboratory analytes.
15. Hematology includes complete blood count (with red blood cell count, total white blood cell count with differential counts, platelet count, hemoglobin, and hematocrit). See Protocol Appendix B for a full list of clinical laboratory analytes.
16. Urinalysis includes urine dipstick analysis for leukocytes, nitrites, or a catalase test of the urine specimen, microscopic evaluation, specific gravity, and pH. See Protocol Appendix B for a full list of clinical laboratory analytes.
17. Urine sample should be collected by clean-catch midstream or other appropriate method that minimizes risk of bacterial contamination.

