##### **5.1.2. Clinical Outcome**

Based on the assessment of signs and symptoms, the Investigator will choose 1 of the following clinical outcomes at the Day 5, EOT, and TOC Visits:

Clinical cure: complete resolution or significant improvement of signs and symptoms of cUTI or AP that were present at baseline and no new symptoms, such that no further antimicrobial therapy is warranted.

Clinical failure: symptoms of cUTI or AP present at study entry have not significantly improved or completely resolved, or new symptoms of cUTI or AP have developed and require the initiation of a non-study antibacterial drug therapy, or death.

Clinical indeterminate: insufficient data are available to determine if the patient is a cure or failure.

Based on the assessment of signs and symptoms, the Investigator will choose 1 of the following clinical outcomes at the LFU Visit:

Sustained clinical cure: met criteria for clinical cure at the TOC Visit and the LFU Visit.

Relapse: clinical cure at the TOC Visit but signs and symptoms of cUTI or AP are present at the LFU Visit.

Clinical failure: clinical failure at the TOC Visit carried forward to the LFU Visit or death between the TOC Visit and LFU Visit.

Clinical indeterminate: insufficient data are available to determine if the patient is a sustained clinical cure or clinical relapse.

Note: if a patient is a clinical failure at EOT, the patient is automatically considered a failure at the TOC and LFU Visits, and an assessment of clinical response by the Investigator will be listed as “failure at EOT.”

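### Does the SAP 8.2 carry-forward of an earlier clinical failure leave the Test-of-Cure outcome open to two scorings that need a change to the plan?

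*SAP*

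**What the plan says.** SAP 8.2, on dropouts and missing data, first counts indeterminate overall responses as failures in the primary analysis. It then adds: "A clinical failure occurring at an earlier time point will be carried forward to the subsequent visits".

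SAP 5.1.2 is narrower: "if a patient is a clinical failure at EOT, the patient is automatically considered a failure at the TOC and LFU Visits". Footnote 10 of SAP Table 1 has the same rule ("If a patient is a clinical failure at EOT, the patient is automatically considered a failure at the TOC and LFU Visits"), as do Protocol 6.4 and 7.6. Protocol 6.5 repeats it for the Late Follow-up (LFU) Visit and has the Investigator's entry there read "failure at EOT or TOC". The LFU definitions in SAP 5.1.2 and Protocol 7.6 also carry a TOC failure to LFU.

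Clinical outcome is rated before EOT as well. Under SAP 5.1.2, "the Investigator will choose 1 of the following clinical outcomes at the Day 5, EOT, and TOC Visits". Protocol 6.3.7 has the item "Assess clinical outcome (Day 7 and EOT Visit only"), which adds a pre-EOT rating for patients treated beyond Day 7. One limb of the failure definition is that "symptoms of cUTI or AP present at study entry have not significantly improved or completely resolved".

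SAP 3.1 sets a minimum exposure: "All patients should receive at least 8 doses of IV study drug before the Investigator considers the patient to be a clinical failure". The same sentence goes on to pair that judgement with taking the patient off study drug.

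**The concern.** Read literally, SAP 8.2 covers a failure at any earlier rating, including Day 5. Suppose a slow responder is rated failure on Day 5, stays on drug, and is cured with eradication at EOT and TOC. The literal text makes this patient an overall failure. If the sentence only fills gaps, as its section heading suggests, the patient is an overall success, which is also the result under the notes that name EOT. Two programmers could therefore code the primary efficacy endpoint (overall success, m-MITT, TOC) and clinical cure at TOC differently. If the choice were left until after unblinding, it could be made with the results in view. Protocol 9.2.2.1 and SAP 8.11.1 restate the treatment of indeterminate outcomes but not the carry-forward sentence, so they do not resolve it.

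**Working it through.** **1. Which failures are open?**

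| Failure rated at | Effect on TOC | Effect on LFU | Settled? |
|---|---|---|---|
| EOT, including an EOT visit held on early stopping | automatic failure | automatic failure | yes (SAP 5.1.2, Table 1 footnote 10; Protocol 6.4, 7.6) |
| TOC | is the TOC outcome | carried forward | yes (SAP 5.1.2; Protocol 7.6) |
| Day 5, or Day 7 if treated longer, with drug stopped for failure | EOT procedures are done then, so an EOT failure | as EOT failure | yes |
| Day 5, or Day 7 if treated longer, with drug continued | SAP 8.2 only | SAP 8.2 only | no |

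Only the last row is open. The EOT notes do not say that EOT is the only source, so SAP 8.2 is broader than they are but does not contradict them.

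**2. Can the open row occur?** Yes. At one dose every 6 hours, the doses due before Day 5 number 4 × 4 = 16 if dosing starts early on Day 1, and 1 + 3 × 4 = 13 if it starts in the last 6 hours of Day 1. Both exceed 8. The documents give no expected number of such patients.

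**3. Effect if the rule only fills missing outcomes.** A missing TOC outcome moves from indeterminate to failure. Both are non-successes with the patient in the denominator, so the change in m-MITT successes is 0. The split between failure and indeterminate can change. So can entry to the CE Population, which excludes an indeterminate TOC response.

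**4. Effect if the rule is literal.** Each affected patient lowers the arm's rate by 100/n points. Inputs are 80 patients at 2:1 (SAP 4). The 80% and 70% m-MITT shares and the success rate near 80% are assumptions. The half-width of the continuity-corrected interval is 1.96·√(p₁q₁/n₁ + p₂q₂/n₂) + 0.5·(1/n₁ + 1/n₂).

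| m-MITT (active/placebo) | Points per patient | Assumed successes | Half-width (points) | One patient as share of half-width |
|---|---|---|---|---|
| 53/27 (all 80) | 1.9 / 3.7 | 42 / 22 | 21.1 | 9% / 18% |
| 43/21 (80%) | 2.3 / 4.8 | 34 / 17 | 24.3 | 10% / 20% |
| 37/19 (70%) | 2.7 / 5.3 | 30 / 15 | 26.2 | 10% / 20% |

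For the first row: 1.96·√(0.1645/53 + 0.1509/27) + 0.5·(1/53 + 1/27) = 0.183 + 0.028 = 0.211.

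**5. Effect on the difference.** If affected patients follow the 2:1 allocation (2 and 1), the shift is −2/53 + 1/27 = −0.1, −2/43 + 1/21 = +0.1, and −2/37 + 1/19 = −0.1 points. An uneven split matters more. At 53/27 the assumed starting difference is −2.2 (95% CI −23.3 to 18.8). Two placebo patients alone move it to +5.2 (−17.4 to 27.8); two ETX2514SUL patients alone move it to −6.0 (−27.5 to 15.5). All three intervals include zero by a wide margin.

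**The case for a change.** The case for a change is not empty. The Day 5 rating offers only cure, failure and indeterminate. There is no category for improving, and indeterminate is kept for insufficient data. Cure also requires that no further antimicrobial therapy be warranted, which is an awkward test partway through a 7-day course. Some patients who later do well could therefore be marked failure on Day 5. The plan also shows that it can write this kind of rule precisely: a microbiologic persistence at EOT counts as persistence at TOC, with both visits named (SAP 5.1.4.1). Naming the visits in SAP 8.2 would take two or three sentences.

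It stands that the sentence is looser than its neighbours and that the open row can occur. It does not follow that the plan must change. An explicit rule would have to choose between two defensible scorings. Letting an observed EOT or TOC outcome prevail would reverse the literal text of SAP 8.2, which is the stricter option. Carrying every pre-EOT failure forward would extend the EOT notes. Reasonable statisticians would differ, and neither choice corrects an error.

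Two limits apply to both sides. The outcome row of SAP Table 1, as available to me, shows no Day 5 entry, but its layout may have been lost in conversion, so I give this no weight. SAP 8.11.4, on exploratory endpoints, is listed in the contents but its text is not visible, so any Day 5 rule there cannot be checked.

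**Conclusion.** This is a gap in wording that analysts can fill sensibly; no change to the plan follows. Carry-forward is settled for EOT and TOC failures. What remains is a pre-EOT failure in a patient kept on drug who is a success at TOC. That pattern is unusual, since the plan ties a failure judgement to stopping drug, and the number affected may be zero.

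The effect is nil on the m-MITT success rate under the fill-missing reading. Under the literal reading it is 1.9 to 2.7 points (ETX2514SUL) or 3.7 to 5.3 points (placebo) per affected patient, which is 9% to 20% of the interval half-width. These figures rest on the assumed m-MITT shares of 70% to 100%, and the percentages also on success near 80%. The primary objective is safety, efficacy is summarised descriptively, and no power calculation or decision rule depends on the scoring. The analyst can record the chosen reading in the programming specification while still blinded; patients with the pattern can be counted across both arms combined at that stage.

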### **8.3. Baseline Definition**

For microbiological data, baseline pathogen(s) are determined from all specimens collected prior to the first dose of study drug.

For all efficacy and safety endpoints, baseline is defined as the last measurement or assessment prior to the first dose of study drug.

### **8.4. Patient Disposition**

Patient disposition will be summarized for the ITT and MITT Populations for each treatment group and in total. The following patient disposition categories will be included in the summary for the ITT and MITT Populations:

- Patients who were randomized,
- Patients who received study drug,
- Patients who did not receive study drug,
- Patients who completed the study treatment,
- Patients who did not complete the study treatment,
- Patients who completed the study, and
- Patients who did not complete the study.

For patients who did not complete the treatment, and patients who did not complete the study, a summary will be provided by reason of discontinuation. A summary of screen failures and the reason for screen failures will be provided. In addition, the reason(s) for exclusion from an analysis population (m-MITT, CE, and ME) will be summarized by treatment group and a corresponding listing will be provided showing each patient's inclusion/exclusion from each population and reason(s) for exclusion.

### **8.5. Protocol Deviations**

The number of patients with at least one reportable protocol deviation, and the number of patients with at least one reportable deviation in each category will be presented by treatment group and overall for the ITT Population.

### **8.6. Demographic and Baseline Characteristics**

Demographic and baseline characteristics will be summarized descriptively for the ITT, MITT, m-MITT, CE, and ME Populations by treatment group and overall. Age, weight, height, body mass index (BMI), and screening creatinine clearance will be summarized descriptively (n, mean, standard deviation, median, minimum, and maximum). Sex, race, ethnicity, age group (<65, 65- <75, and ≥75 years) and screening creatinine clearance group (<30 mL/min, 30- <70 mL/min and ≥70 mL/min) at baseline will be summarized with contingency tables.

### **8.7. Baseline Infection Characteristics**

Baseline infection characteristics will be summarized with descriptive statistics for the ITT, MITT, m-MITT, CE, and ME Populations. Infection type (cUTI or AP) will be summarized to show the

number and percentage of patients in each category. Signs/symptoms and evidence of pyuria criteria the patient met at enrolment will be summarized by infection type with contingency tables. Risk associated with cUTI will also be summarized for patients with cUTI.

All baseline pathogens will also be summarized for the m-MITT and ME Populations.

The number and percentage of patients with each sign and symptom present at baseline (urinary frequency, urinary urgency, dysuria, nausea, vomiting, abdominal pain, suprapubic pain or discomfort, flank pain, and costo-vertebral angle tenderness, by severity (absent, mild, moderate and severe), will be tabulated for the MITT, m-MITT, CE and ME Populations. Additional tables will summarize each sign and symptom at baseline separately for patients with cUTI and AP in the MITT, m-MITT, CE and ME Populations.

### **8.8. Medical History**

Medical history of renal/urological conditions will be summarized descriptively by treatment group and in total for MITT and m-MITT Populations. All other medical and surgical history will be summarized for the MITT and m-MITT Populations for each treatment group and in total by system organ class (SOC) and preferred term (PT).

All Medical and surgical history will be listed by patient.

### **8.9. Prior and Concomitant Medications**

Prior medications are medications used before the first dose of study drug. Concomitant medical are medications used on or after the first dose of study drug.

The prior and concomitant medications will be summarized with the number and percentages by Anatomical Therapeutic Chemical (ATC) class and preferred term for each treatment group and overall in the m-MITT Population. Although a patient may have taken two or more medications, the patient is counted only once within an ATC classification. The same patient may contribute to two or more preferred terms in the same classification.

The proportion of patients who receive the prior and concomitant medications will be summarized by treatment group and overall for the following:

- Systemic antibacterial medications taken prior to (within 14 days) the first dose of study drug,
- Systemic antibacterial medications taken within 72 hours prior to the first dose of study drug,
- Non-antibacterial medications taken prior to (within 14 days) the first dose of study drug, and
- Concomitant medications taken on or after the first dose of study drug.

All prior and concomitant medications and procedures will be listed by patient.

### **8.10. Dosing and Extent of Exposure**

Descriptive statistics for the duration of study drug will be summarized by treatment group for the Safety, m-MITT, CE, and ME Populations. Treatment duration is defined as the date of the last dose of study medication - first dose of study medication +1 day. The number and percentage of patients receiving 1-3, 4-6, 7, 8-10 and 11-14 days of study drug will be provided. The total number of doses of study drug received will also be summarized by treatment group using descriptive statistics.

Compliance with study drug will be summarized, and will be defined as the total number of doses of study drug taken, divided by the total number of doses expected multiplied by 100. Total number of expected doses will be derived based on elapsed time between first and last doses of study drug and its prescribed frequency. Percent compliance as a continuous variable and the proportion of patients with <80% and  $\geq$ 80% compliance will be summarized by treatment group for the Safety, m-MITT, CE and ME Populations.

